7.4 Evaluation of pharmacodynamics

Statistical analysis

The PK parameters will be listed only.

8. Evaluation of Safety

8.1 Adverse events

Definitions and data conventions

Pre-treatment adverse events

An AE will be classified as pre-treatment AE if it starts before the date/time of first study medication intake (AE onset date/time < date/time of first study medication intake).

Treatment-emergent adverse event (TEAE)

An AE will be classified as a TEAE if it starts on or after the date/time of first study medication intake (AE onset date/time \geq date/time of first study medication intake).

In case of missing or incomplete dates/times not allowing a direct allocation to any of the two categories of AEs, a worst-case allocation will be done according to the available parts of the onset and the end dates/times. The AE will be allocated to the first category allowed by the available data, according to the following order:

- TEAE
- Pre-treatment.

Serious adverse event (SAE)

A SAE is an AE judged as serious.

Adverse drug reaction (ADR)

An ADR is an AE judged as “Possibly Related”, “Probably Related” or “Definitely Related”.

Adverse event leading to discontinuation

An AE leading to discontinuation is an AE with action taken equal to “Study drug withdrawn and /or patient withdrawn from the study”.

Adverse event leading to death

An AE leading to death is an AE with outcome equal to “Fatal”.

| Forms | | | |
|--------------|--|------------------------------------|----------------|
| Title | | Statistical Analysis Plan Template | |
| Code | | Version | Effective Date |
| FRM_ST03_032 | | 01 | 23 Apr 2015 |
| | | 27 of 31 | |

Count of adverse events

Two AEs with the same Preferred Term (PT) and classified in the same category (pre-treatment AE or TEAE) will be considered as two different events when calculating the “number of events” in the tables.

Statistical analysis

Pre-treatment AEs and TEAEs will be presented separately. Pre-treatment AEs will be presented in the listings only.

The number of treatment-emergent AEs, SAEs, ADRs, serious ADRs, severe AEs, AEs leading to discontinuation and AEs leading to death, and the number and the percentage of patients experiencing treatment-emergent AEs, SAEs, ADRs, serious ADRs, severe AEs, AEs leading to discontinuation and AEs leading to death will be summarised by cohort.

AEs will be coded using the MedDRA dictionary (version 19.0). The SOCs and PTs will be used for tabulation. The number of AEs and the number and the percentage of patients with at least one AE will be presented by SOC and PT for treatment-emergent AEs, SAEs, ADRs, AEs leading to discontinuation and AEs leading to death by cohort.

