3. STUDY DESIGN

This prospective, multi-centre, open-label, non-randomized, consecutive study will be conducted in accordance with the European Union (EU) Clinical Trial Directive 2001/20/EC and 2005/28/EC, The Medicines for Human Use (Clinical Trials) Regulations 2004 and current amendments, the Declaration of Helsinki (revised version of Edinburgh, Scotland 2000), Good Manufacturing Practice (GMP), Good Clinical Practice (GCP) and the current national regulations and guidelines, approved by both the local ethics committee and regulatory authority.

Eighteen patients older than 18 years of age will be enrolled and receive a single intravitreal injection of PP-001. Patients must have chronic, posterior uveitis, intermediate uveitis or panuveitis requiring treatment and have been receiving an adequate therapy of e.g. systemic corticosteroid treatment or immunosuppressive therapy (e.g. azathioprine, methotrexate, cyclosporine, mycophenolate, tacrolimus) or any combination thereof. Any systemic therapy at study start should *be continued throughout the study*. Patients must have best-corrected Early Treatment Diabetic Retinopathy Study (ETDRS) visual acuity of 10 letters or better

(approximately 1/35 or 0.032) but equal or less than 50 letters (approximately 20/100 or 0.2) in the study eye.

Patients must give written consent for the study before any study assessments are performed. Screening assessments will be performed 8–14 days before dosing. Baseline assessments will be performed no more than 7 days before injection. The study will involve eight study visits (Screening, Baseline, the day of injection (Day 0) and Days 2, 7, 14, 21 and 28) and telephone calls on Day 1 and Day 40.

Patients will be divided into three cohorts of four patients. Patients will receive the following treatments administered as a single intravitreal injection:

- Cohort 1 will receive 0.3 µg of PP-001
- Cohort 2 will receive 0.6 µg of PP-001
- Cohort 3 will receive 1.2 µg of PP-001

The patients within a cohort will be dosed consecutively with a minimum time interval of 7 days between the dosing of the previous patient and the dosing of the next patient. The results from each dosing day will be reviewed before progressing towards the subsequent dosing day. The next cohort will only receive PP-001 after the previous cohort has completed all study sessions up to Day 28 and no safety issues have been identified after reviewed by the Safety data management board (SDMB).

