7. ADVERSE EVENTS

An AE is any untoward medical occurrence in a patient or clinical investigation patient administered a pharmaceutical product that does not necessarily have a causal relationship with this treatment. An AE can therefore be any unfavourable and unintended sign (including an abnormal laboratory finding), symptom, or disease temporally associated with the use of an investigational product, whether or not related to the investigational medicinal product.

Any pre-existing conditions or signs and/or symptoms present in a patient before the start of the study (i.e., before informed consent) should be recorded as medical/surgical history. Any medical occurrences that are new or worsened from the time of informed consent and up to and including the final visit must be reported as AEs or SAEs. All AEs and SAEs must be recorded irrespective of whether they are considered drug-related.

Patients will be monitored throughout the study for adverse reactions to the study medications and/or procedures at each study visit. Questions will be posed in a non-leading manner so as not to bias the response. In addition to questioning at specific time points, patients will be encouraged to report any AEs spontaneously. Any patient with an AE, SAE or clinically significant abnormal laboratory test value will be evaluated by the Investigator, or a monitoring physician, and will be treated and/or followed up until the symptoms or values have resolved or are assessed as stable by the Investigator. A physician, either at the Investigative site or at a nearby hospital emergency room, will administer treatment of any SAEs. Where appropriate, medical tests and examinations may be performed to ensure that an AE has fully resolved.

Adverse events will be monitored throughout the study from the time a patient is consented through the final follow-up visit; SAEs are to be collected from the time of consent through to the follow-up visit. Whenever possible, a specific disease or syndrome rather than individual associated signs and symptoms should be identified by the Investigator and recorded on the patient's eCRF. However, if an observed or reported sign or symptom is not considered a component of a specific disease or syndrome by the Investigator, it should be recorded as a separate AE on the patient's eCRF.

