9.6 Safety Analysis

Safety will be evaluated in the Safety Analysis Set by presenting summaries of AEs and vital signs.

Summary tables will be provided for all TEAEs. A treatment-emergent AE is defined as an AE with a start date and time on or after the first dose of study drug. Adverse events will be coded using the Medical Dictionary for Regulatory Activities (MedDRA®). The number and percentage of patients with TEAEs will be tabulated by system organ class and MedDRA Preferred Term for each treatment group and by severity and relationship to treatment.

Adverse events leading to premature discontinuation from the study drug and serious TEAEs will be presented either in a table or a listing.

Descriptive statistics of vital signs and the change from baseline for each scheduled evaluation will be summarized at each study visit and the worst overall post-baseline value will be provided. The number and percent of patients with treatment-emergent values with potential clinical significance will be tabulated.

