9.3 Tables

The list of tables is provided here below:

| TABLE | TITLE |
|----------------|---|
| TABLE 14.1.1 | SUBJECT DISPOSITION / SUMMARY OF ALL SUBJECTS |
| TABLE 14.1.2.1 | PRIMARY REASONS FOR DISCONTINUATION FROM STUDY / SAFETY SET |
| TABLE 14.1.3.1 | ANALYSIS SETS / SAFETY SET |
| TABLE 14.1.4.1 | DEMOGRAPHIC CHARACTERISTICS / SAFETY SET |
| TABLE 14.1.5.1 | MEDICAL AND OPHTHALMIC HISTORY: PAST DISEASES / SAFETY SET |
| TABLE 14.1.5.2 | MEDICAL AND OPHTHALMIC HISTORY: CONCOMITANT DISEASES // SAFETY SET |
| TABLE 14.1.6.1 | PREVIOUS MEDICATIONS / SAFETY SET |
| TABLE 14.1.6.2 | CONCOMITANT MEDICATIONS / SAFETY SET |
| TABLE 14.2.2.1 | ETDRS SCORES DURING THE STUDY AND CHANGE FROM BASELINE / SAFETY SET |
| TABLE 14.2.2.2 | ETDRS SCORES DURING THE STUDY AND CHANGE FROM BASELINE / PP SET |

| Forms | | | | |
|--------------|--|------------------------------------|----------------|----------|
| Title | | Statistical Analysis Plan Template | | |
| Code | | Version | Effective Date | Page |
| FRM_ST03_032 | | 01 | 23 Apr 2015 | 30 of 31 |

| TABLE | TITLE |
|----------------|---|
| TABLE 14.2.3.1 | SLIT LAMP EXAMINATION DURING STUDY / SAFETY SET |
| TABLE 14.2.4.1 | FLUORESCEIN ANGIOGRAM, ETDRS, VISUALLY EVOKED CORTICAL POTENTIAL, INTRAOCCULAR PRESSURE AND DILATED FUNDOSCOPY DURING STUDY / SAFETY SET |
| TABLE 14.2.5.1 | ELECTRORETINOGRAPHY, OPTICAL COHERENCE TOMOGRAPHY, VISUAL FIELD, CORNEAL ENDOTHELIAL MICROSCOPY, FUNDUS PHOTOGRAPHY AND AMSLER GRID DURING STUDY / SAFETY SET |
| TABLE 14.2.6 | PATIENT- REPORTED OUTCOMES DURING THE STUDY AND CHANGE FROM BASELINE / SAFETY SET |
| TABLE 14.3.1.1 | SUMMARY OF TREATMENT EMERGENT ADVERSE EVENTS / SAFETY SET |
| TABLE 14.3.1.2 | TREATMENT EMERGENT ADVERSE EVENTS BY SYSTEM ORGAN CLASS AND PREFERRED TERM / SAFETY SET |
| TABLE 14.3.1.3 | TREATMENT EMERGENT SERIOUS ADVERSE EVENTS BY SYSTEM ORGAN CLASS AND PREFERRED TERM / SAFETY SET |
| TABLE 14.3.1.4 | TREATMENT EMERGENT ADVERSE DRUG REACTIONS BY SYSTEM ORGAN CLASS AND PREFERRED TERM / SAFETY SET |
| TABLE 14.3.1.5 | TREATMENT EMERGENT ADVERSE EVENTS LEADING TO DISCONTINUATION BY SYSTEM ORGAN CLASS AND PREFERRED TERM / SAFETY SET |
| TABLE 14.3.1.6 | TREATMENT EMERGENT ADVERSE EVENTS LEADING TO DEATH BY SYSTEM ORGAN CLASS AND PREFERRED TERM / SAFETY SET |
| TABLE 14.3.2.1 | HAEMATOLOGY RESULTS DURING THE STUDY AND CHANGE FROM SCREENING / SAFETY SET |
| TABLE 14.3.2.2 | BIOCHEMISTRY RESULTS DURING THE STUDY AND CHANGE FROM SCREENING / SAFETY SET |

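### TEAEs are defined by onset time alone, so an AE that starts before injection and worsens after it is left out of all six AE tables unless the site opens a new record

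*SAP*

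**What the plan says.** The two documents agree with each other. Protocol 9.6 says: "A treatment-emergent AE is defined as an AE with a start date and time on or after the first dose of study drug". SAP 8.1 repeats the test: "An AE will be classified as a TEAE if it starts on or after the date/time of first study medication intake". It adds the complement: "An AE will be classified as pre-treatment AE if it starts before the date/time of first study medication intake". Neither mentions an event that changes after dosing.

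SAP 8.1 then separates the reporting: "Pre-treatment AEs will be presented in the listings only". The first AE table in SAP 9.3 (14.3.1.1) is titled "SUMMARY OF TREATMENT EMERGENT ADVERSE EVENTS / SAFETY SET". The titles of 14.3.1.2 to 14.3.1.6 (SOC/PT, serious events, adverse drug reactions, discontinuations, deaths) carry the same treatment-emergent restriction.

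Collection starts earlier than dosing. Protocol 7 says: "Adverse events will be monitored throughout the study from the time a patient is consented through the final follow-up visit". It also makes reportable "Any medical occurrences that are new or worsened from the time of informed consent", up to the final visit.

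**The concern.** The recording window opens before injection. Protocol 3 places screening 8 to 14 days before dosing, and Table 1 allows it from Day -14 up to dosing. In that window the patient has fluorescein angiography with dilating drops, electroretinography with anaesthetic drops, a speculum and an electrode on each eye, and contact tonometry. The eyes have chronic uveitis that requires treatment. An AE open at the time of injection is therefore plausible.

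If such an event becomes severe or serious after injection, that change is what a first-in-human safety study needs to count. AEs are a named part of the primary endpoint (Protocol 2.1, SAP 3.5.1). An onset-only rule looks at when the record began and ignores what happened after dosing. With four patients per dose, one omitted patient can decide what a table row shows.

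**Working it through.** The plan gives no figure on this point, so there is none to reproduce. The check applies the written rule to cases and follows them through to the tables.

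**Inputs**
- TEAE and pre-treatment definitions: SAP 8.1, Protocol 9.6.
- Start of AE collection (consent): Protocol 7.
- AE tables and listings: SAP 9.3 and 9.5.
- Cohort size of four, three cohorts: Protocol 3, SAP 3.1.

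**Step 1. Apply the rule.** Let t be the onset day and w the day of worsening, with injection at day 0.
- Rule as written: TEAE if t ≥ 0, otherwise pre-treatment.
- Rule with a worsening clause: TEAE if t ≥ 0 or w ≥ 0.

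| Onset | Worsening | As written | With worsening clause |
|---|---|---|---|
| Day -10 | none | pre-treatment | pre-treatment |
| Day -10 | Day 3 | pre-treatment | TEAE |
| Day -1 | Day 1 | pre-treatment | TEAE |
| Day 0 (after injection) | none | TEAE | TEAE |
| Day 2 | none | TEAE | TEAE |

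Only events open at injection that worsen afterwards change class.

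**Step 2. Follow them to the output.** Under the written rule the second and third cases count in 0 of the 6 AE tables and appear only in Listing 16.2.7.1. This holds even if the event is serious, severe or judged related, because the serious-event and drug-reaction tables are also restricted to treatment-emergent events.

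**Step 3. Look for another clause that rescues them.**
- The worst-case allocation to TEAE in SAP 8.1 applies only when dates or times are missing or incomplete. A complete pre-injection onset does not trigger it.
- The reporting rule in Protocol 7 measures worsening from consent. It brings a worsened pre-consent condition into AE reporting. It does not say that an AE already on the eCRF gets a second record, or a new onset date, when it worsens after injection.
- Protocol 7 asks for severity, onset, duration and outcome for each AE, with no rule for a later change in severity.
- SAP 8.1 counts two AEs with the same preferred term as two events, but only once two records exist.

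**Step 4. Size per patient.**
- Cohort of four: 1/4 = 25 percentage points.
- Three cohorts together: 3 × 4 = 12 patients, and 1/12 = 8.3 points.

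The shift applies to any row in which that patient is not already counted. A patient with another TEAE leaves the any-TEAE row unchanged, but can still move the severe, serious or drug-reaction row, or the row for that preferred term.

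**The case against.** The strongest reply is that collection may already handle this. Protocol 7 can be read as making a post-injection worsening a reportable AE in its own right, with its own onset and hence TEAE status. The eCRF and its instructions, which are not among the documents, may say so. An investigator who attributes a worsening to PP-001 also has reason to open a new record, because causality is judged on timing relative to the drug. This is a fair possibility. It remains one reading, however, and no sentence in either document requires it. In a multi-centre study run under several country protocols, sites could differ, and the same event would then be counted at one site and not at another.

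Several stronger conclusions are tempting, and the documents do not support them.
- **That the event disappears from all safety output.** It does not. Intraocular pressure, slit-lamp findings, fundoscopy and visual acuity are tabulated by visit and cohort (14.2.x), as are laboratory values and vital signs (14.3.2.x, 14.3.3.1). The AE listing can be read in full for a study of this size.
- **That dosing decisions are compromised.** The stopping criteria in Protocol 6.14.3 and SAP 3.1 refer to related AEs and SAEs without any treatment-emergent restriction, and the board's review in Protocol 10.2 covers AEs generally.
- **That every omission hides a drug effect.** Compared with the wider definition, the rule can only lower TEAE counts. But it also omits worsening due to the underlying uveitis, and the incomplete-date rule errs towards TEAE.
- **That the number affected can be estimated.** If 10% to 30% of patients had an open ocular AE at injection and one third of these worsened, 12 × 0.10 × 1/3 = 0.4 to 12 × 0.30 × 1/3 = 1.2 patients would be misclassified. Those rates are assumptions without support in the documents, and the lower end is compatible with no case at all.

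**Conclusion.** The gap is real and is shared by both documents, so it is not a contradiction between them. As written, an AE that starts between consent and injection and becomes more severe or serious afterwards is pre-treatment, and is absent from Tables 14.3.1.1 to 14.3.1.6, unless a site chooses to open a new record. The consequence is confined to the AE tables in the report.

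The 25-point and 8.3-point figures rest only on the planned cohort size, and on the patient not already being counted in the row concerned. That the worsening clause is missing is certain. How often it would matter is unknown: it depends on how many AEs are open at injection, how many of these worsen, and how sites record the change.

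**What to change.** In SAP 8.1 and Protocol 9.6, define a TEAE as an AE that starts at or after injection, or that was present before injection and increases in severity or becomes serious at or after injection. Use this definition in all six AE tables.

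Have sites record such a worsening as a new AE line dated at the worsening, so that the definition can be programmed from the onset field.

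SAP 4.8 says the study is to close at cohort 3, so a site instruction may come too late. If enrolment has ended, list every AE with onset before injection that was still open at injection, query whether and when it worsened, and classify these events before database lock. The data review in SAP 4.9 is a natural place for this.

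The cost is one sentence in each document, one line of site instruction and a few queries. It would be wrong to assume that no new data are needed: if only one severity and one onset were entered per event, the date of worsening has to be obtained. No extra patients are needed, and no visit or treatment rule changes.

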Variables for Analysis:**Primary**

- Safety parameters (i.e., changes in clinical signs and symptoms from ophthalmic exam, and AEs)

Secondary

- Improvement of inflammation or of any other parameter determined at the ophthalmic examination following the injection of PP-001
- The concentration of PP-001 in plasma at Screening, 4 h ± 1 h after dosing and on Day 2

Safety analysis

The incidence of treatment-emergent adverse events (TEAEs), SAEs, deaths and discontinuations of study drug due to an AE or SAE will be summarized by System Organ Class and Preferred Term according to the Medical Dictionary for Regulatory Activities, by relationship to study drug, and by severity. The incidence of potentially clinically significant vital signs will be summarized.

Pharmacokinetic analysis

The concentration of PP-001 in plasma will be measured in blood samples taken at Screening, 4 h ± 1 h after dosing and on Day 2.

Table 1. Schedule of Assessments and Procedures

| Phase | Screening | Baseline ⁱ | Pre injection | Post injection | Telephone call ^a | Safety visits | | | | | Telephone call ^a |
|--|------------------|-----------------------|---------------|------------------|-----------------------------|---------------|-----------|------------|------------|-------------------------|-----------------------------|
| Day | -14 up to dosing | -7 up to dosing | 0 | 0 | 1 | 2 | 7 +/-1 | 14 +/-1 | 21 +/-1 | 28 ^h +/-1 | 40 |
| Electroretinography | | X | | | | | | X | | X | |
| Fluorescein angiogram | X | | | | | | | | | X | |
| Optical coherence tomography | | X | | | | X | X | X | X | X | |
| Best corrected visual acuity (ETDRS) | X | X | | | | X | X | X | X | X | |
| Visual field (computerized, 30°) | | X | | | | | X | | | X | |
| Visually evoked cortical potential | X | | | | | | | | | X | |
| Intraocular pressure | X | X | | X ^b | | X | X | X | X | X | |
| Slit lamp examination ^c | X | X | X | X ^b | | X | X | X | X | X | |
| Dilated fundoscopy ^d | X | X | | X ^b | | X | X | X | X | X | |
| Study drug injection | | | | X | | | | | | | |
| Blood sampling for PK analysis | X | | | X ^{b,e} | | X | | | | | |
| Corneal endothelial microscopy | | X | | | | | X | | | X | |
| Fundus photography | | X | | | | | | | | X | |
| Amsler grid | | X | | | | X | X | X | X | X | |
| Medical and ophthalmic histories | X | X | | | | | | | | | |
| Vital signs ^f | X | X | X | | | X | X | X | X | X | |
| Twelve-lead electrocardiogram | X | | | | | | | | | X | |

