6.14.3 Study Stopping Criteria

Dosing of further patients will be stopped if the following criterion is observed:

- A moderate or severe AE classified as being possibly, probably or definitively study-drug related or potential major safety concerns as identified by the Investigator after consultation with the SDMB are reported in more than 50% of patients in the same cohort.

Dosing will be stopped or the dose decreased if:

- One patient on any dosing day shows a possibly, probably or definitively study-drug-related SAE judged by the Investigator after consultation with the SDMB or other potential major safety concerns are identified by the Investigator in agreement with the SDMB.

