The patients within a cohort will be dosed consecutively with a minimum time interval of 7 days between the start of injection of the previous patient and start of injection of the next patient. The results from each dosing day will be reviewed before progressing with the subsequent dosing day. The next cohort will only commence with dosing after the previous cohort has completed all study sessions up to Day 28 and no safety issues have been identified after being reviewed by the safety data management board (SDMB).

After 12 patients have been treated in the three cohorts and after all patients have finished the last follow up an interim analysis by the SDMB will be conducted to identify potential safety issues and to determine the highest tolerable dose. If no safety issue can be identified, then a fourth, higher dose will be given to a cohort of four patients (Cohort 4). The dose for a potential Cohort 4 will be 2.1 µg of PP-001. (Note: Interim analysis and dosing of a fourth cohort will not be performed). If safety issues are identified in any of Cohorts 2, 3 or 4, two additional patients will receive the next lower dose.

Dosing of further patients will be stopped if the following criterion is observed:

- A moderate or severe AE classified as being possibly, probably or definitively study drug related or potential major safety concerns as identified by the Investigator after consultation with the SDMB are reported in more than 50% of patients in the same cohort.

Dosing will be stopped or the dose decreased if:

- One patient on any dosing day shows a possibly, probably or definitively study-drug related SAE judged by the Investigator after consultation with the SDMB or other potential major safety concerns are identified by the Investigator in agreement with the SDMB.

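### The SAP omits, without declaring it, safety tables that Protocol 9.6 commits to: TEAEs by severity, patients with potentially clinically significant vital signs, and the worst post-baseline vital-sign value

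*SAP*

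**What the plan says.** **Protocol.** Under Protocol 9.6, patients with TEAEs "will be tabulated by system organ class and MedDRA Preferred Term for each treatment group and by severity and relationship to treatment". For vital signs the same section says that "the worst overall post-baseline value will be provided", and then: "The number and percent of patients with treatment-emergent values with potential clinical significance will be tabulated." The safety paragraph of the synopsis repeats two of these commitments. It wants AE incidence "by relationship to study drug, and by severity", and adds: "The incidence of potentially clinically significant vital signs will be summarized."

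**SAP.** SAP 8.1 plans an overview by cohort with one severity item, the count of severe AEs whatever their cause. It then plans tables in which AE counts "will be presented by SOC and PT for treatment-emergent AEs, SAEs, ADRs, AEs leading to discontinuation and AEs leading to death by cohort". An ADR is any AE judged possibly, probably or definitely related, of any grade. SAP 8.3 plans descriptive statistics of blood pressure and heart rate, and of their changes from baseline, at each visit. SAP 8.6 foresees no other safety evaluation. The table list in SAP 9.3 agrees with this: Tables 14.3.1.1 to 14.3.1.6 for AEs and Table 14.3.3.1 for vital signs.

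SAP 4.8 lists four changes from the protocol: the ITT set is dropped and the PP set redefined, visual acuity replaces vitreous haze, cohort 4 is removed, and there is no interim analysis. None concerns the safety tables.

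**The concern.** Safety and tolerability of ascending doses is the primary objective, and AEs are part of the primary endpoint. In cohorts of four, the useful information is often the grade of the related events and whether it rises with dose. The protocol promises a severity breakdown, the SAP's table list has none, and nothing tells the reader that it was dropped.

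The trial itself treats the mild/moderate boundary as important. The stopping criterion in Protocol 6.14.3 counts "A moderate or severe AE classified as being possibly, probably or definitively study-drug related or potential major safety concerns", and SAP 3.1 repeats the threshold that these "are reported in more than 50% of patients in the same cohort". A reader of the final tables who wants to see how close each dose came to that criterion would find related events pooled over all grades.

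The vital-sign outputs matter less, because negligible systemic exposure is expected after intravitreal dosing. They are still protocol commitments.

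**Working it through.** The plan states no figure on this point to reproduce. The check is a comparison of texts, followed by a small count to show what the planned tables can and cannot separate.

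**Step 1. Commitments against planned outputs.**

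| Commitment in Protocol 9.6 | Planned in the SAP | Declared in SAP 4.8 |
|---|---|---|
| TEAEs by SOC/PT, by severity | One overall row of severe AEs, any cause (8.1); no mild or moderate grades; no severity by SOC/PT | No |
| TEAEs by relationship | Kept as related versus all: ADR tables (8.1, Table 14.3.1.4) | Not needed |
| n (%) with potentially clinically significant vital signs | None (8.3, 8.6, Table 14.3.3.1) | No |
| Worst post-baseline vital-sign value | None as such; per-visit minimum and maximum only (4.1, 8.3) | No |

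**Step 2. Example.** Inputs: three cohorts of four patients (SAP 3.1) and the overview rows of SAP 8.1. Suppose that two patients per cohort have one related TEAE each, that there are no other AEs, and that none is severe, serious, fatal or leads to discontinuation. In scenario A all events are mild. In scenario B those at 1.2 µg are moderate.

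| Row | 0.3 µg | 0.6 µg | 1.2 µg, A | 1.2 µg, B |
|---|---|---|---|---|
| Patients with a TEAE | 2/4 | 2/4 | 2/4 | 2/4 |
| Patients with an ADR | 2/4 | 2/4 | 2/4 | 2/4 |
| Number of TEAEs / ADRs | 2 / 2 | 2 / 2 | 2 / 2 | 2 / 2 |
| Patients with a severe AE | 0/4 | 0/4 | 0/4 | 0/4 |
| *Not planned:* patients with a moderate event | 0/4 | 0/4 | 0/4 | 2/4 (50%) |

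Every planned row is the same in A and B. A severity table would separate them.

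**Step 3. With no severe AEs.** Each related event may then be mild or moderate without changing any planned patient or event count. If *a* patients have an ADR, the number with a moderate related event can be any whole number from 0 to *a*. The threshold is more than 0.5 × 4 = 2 patients, so at least 3 of 4.

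- *a* = 2: 0, 1 or 2 patients. The AE part of the criterion cannot have been met.
- *a* = 3: 0, 1, 2 or 3 patients. The tables do not show whether 3 was reached.
- *a* = 4: 0, 1, 2, 3 or 4 patients. The same holds.

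**Step 4. When AEs are severe.** SAP 8.1 also reports numbers of events. If the number of TEAEs equals the number of ADRs, every severe AE is related, so at least as many patients have a moderate or severe ADR as have a severe AE. With ADRs in 4/4 and severe AEs in 3/4, the count is then at least 3. The ambiguity is therefore greatest when few or no AEs are severe.

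**Step 5. Vital signs.** SAP 4.1 gives n, mean, SD, median, minimum and maximum. With four non-missing values, the middle two are M − d and M + d, where M is the median, and d follows from

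3·SD² = (min − m)² + (max − m)² + 2(M − m)² + 2d², with mean m = (min + max + 2M)/4.

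Up to rounding, all four values at a visit, and all four changes, can be recovered. Patients cannot be linked across visits. If exactly one of four exceeds a limit at each of three visits, the number of distinct patients is 1, 2 or 3 (25%, 50% or 75%), and the per-visit statistics do not say which.

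**The case against.** The strongest case on the other side is that little is lost. With four patients per cohort and a single dose, grades can be counted by hand from Listing 16.2.7.1, and vital-sign exceedances from Listing 16.2.8.5. The cohort's most extreme vital-sign value can be read from the per-visit minimum and maximum. Protocol 9 leaves the description of the analysis to the SAP. The table shells are in a separate appendix that was not available, and the overview table could carry severity rows. The SAP covers national protocols from five countries, of which one was supplied.

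Much of this stands, and it limits the point to reporting. It does not remove it. SAP 9.1 has tables programmed independently and listings only peer-reviewed, so a hand count from a listing gets the weaker check. The SAP text itself names the tabulations it plans, and none is by grade. Leaving the description to the SAP does not make silence a declared change, since SAP 4.8 exists for that purpose.

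A reader might infer that moderate related AEs appear in no table, or that Protocol 9.6 promises severity crossed with relationship. Neither is supported. Moderate related AEs are included, ungraded, in Table 14.3.1.4. The protocol wording can be read as two separate breakdowns, in which case its own severity table would show the moderate or severe related count only if no patient had an unrelated event of that grade.

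**Conclusion.** The point holds as an undeclared omission of protocol-specified safety outputs. The severity breakdown is the part that matters, the count of patients with potentially clinically significant vital signs comes second, and the worst value is minor. When no AE is severe, the planned tables cannot separate mild from moderate related events by dose. In the example this is the difference between 0/4 and 2/4 patients with a moderate related event at 1.2 µg.

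A stronger reading would be that the stopping rule could not be operated. The documents do not support it. The investigator and the SDMB apply the rule during dosing from patient data, and it also covers potential major safety concerns that no AE table would capture. What suffers is the reporting and later verification of tolerability. Nor can it be said that the tables never settle the count, because the event numbers can do so when severe AEs are common.

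The conclusion rests on the SAP text and table titles without the shells, and on one national protocol. The arithmetic assumes four patients per cohort; if two patients were added at a lower dose, the denominator there would be 6 and the threshold at least 4. The omission should be corrected, but it does not threaten the validity of the trial.

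**What to change.** 1. In SAP 8.1 and 9.3, add a by-cohort table of TEAEs by SOC/PT and maximum severity (mild, moderate, severe), shown once for all TEAEs and once for ADRs. The first part meets the protocol commitment. The ADR part is a useful addition that gives the number of patients with a moderate or severe related event; Protocol 9.6 does not clearly require it.
2. In SAP 8.3 and 9.3, add the number and percent of patients per cohort with a treatment-emergent vital sign beyond stated limits, and the worst post-baseline value. Protocol 9.6 names no limits. Those in Protocol Appendix 2 are the natural choice: systolic change above 30 mmHg, diastolic change above 20 mmHg, and the heart-rate limits by posture.
3. Declare and justify in SAP 4.8 any of these outputs that will not be produced.

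The cost is a little extra programming from data already collected, or one sentence for each output withdrawn. Trial conduct and sample size do not change.
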